Main objective and primary endpoint	To compare the effect hydrocortisone plus fludrocortisone vs. placebo on a composite of death or persistent organ dysfunction – defined as continued dependency on mechanical ventilation, new renal replacement therapy, or vasopressors – assessed at 90 days on intensive care unit (ICU) adults and having different biological profiles for immune responses and corticosteroids bioactivity The primary endpoint is death or persistent organ dysfunction (defined as continued dependency on mechanical ventilation, renal replacement therapy, or vasopressors) and with SOFA score >6 up to 90 days.						
Secondary objectives	 Mortality and health-related quality of life at 6 months; 						
and endpoints	 Daily organ function (SOFA score days 1, 2, 3, 4, 7, 10, 14, 28, and 90); 						
	 Daily secondary infections (up to 90 days) Daily blood and urinary levels of glucose, sodium and potassium (up to 28 day) Daily gastroduodenal bleeding (up to 28 day) Daily cognitive function and muscles' strength (days 1 to 28, 90 and 180 days) 						
Study design	Multi-arms Parallel blinded randomized controlled trial preceded						
	by a 6-month run-in observational period. Observational phase (run-in period) Interventional phase. 						
Inclusion Criteria	1. Patients ≥18 years old;						
observational phase: (N°1,2,3,4,6,7,8,9) interventional phase:	 Admitted to ICU with proven or suspected infection as the main diagnosis; Community acquired pneumonia related sepsis OR vasopressors dependency (norepinephrine, epinephrine, vasopressin, dopamine, phenylephrine) OR septic shock (Singer 2016: vasopressor to maintain mean blood pressure of at least 65 mmHg and lactate levels above 2 mmol/l) OR acute 						
(N°1,2,3,4,5,6,7,8).	 respiratory distress syndrome (ARDS – Ranieri 2012: a- acute onset, i.e. within one week of an apparent clinical insult and with progression of respiratory syndrome, b- bilateral opacities on chest imaging not explained by other pulmonary pathologies, e.g. pleural effusion, atelectasis, nodules etc, c-no evidence for heart failure or volume overload, d- PaO2/FiO2 ≤ 300 mm Hg, - PEEP ≥ 5 cm H2O Patient who has signed an informed and written consent whevener he/she is able of consent, if not, if not ascent from his/her representant whenever he/she is present at time of screening for inclusion 						

	5. Patients who have been tested for one or more RECORDS
	specific biomarkers:
	a. CIRCI
	b. Endocan
	c. GILZ
	d. CPD

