2.2 SECONDARY OBJECTIVES OF EACH ANALYSIS BY BIOLOGICAL MARKER

- To compare the effect of hydrocortisone plus fludrocortisone vs. placebo on:
 - 1) 6-month mortality;
 - 2) 6-month HRQoL;
 - 3) organ function (days 1, 2, 3, 4, 7, 10, 14, and 28 if in ICU);
 - 4) hyperglyceamia as defined by glucose levels of >8.3 mmol/L (150mg/dL) (daily up to day 28)
 - 5) hypernatremia as defined by serum sodium levels of >150mmol/L (daily up to day 28)
 - 6) secondary infection (daily up to day 90)
 - 7) beeding in the gastrointestinal tract defined by clinical evidence of active bleeding and need for blood transfusion OR hemostatic endoscopic or surgical procedures
 - 8) neurological cognitive dysfunction defined as by low score on the PROMIS Adult cognitive function score (appendix 15.4.7)
 - 9) neuromuscular weakness defined as a grade of 2 or more on Muscular Disability Rating Scale (MDRS) (appendix 15.4.6)

[figure not shown]

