5.14.2 Secondary Outcomes

The secondary outcomes will include:

1) Mortality at 7, 14, 28 day and 6 months.

2) Vasopressor free days: defined as the number of days with permanent hemodynamic stability in the absence of any vasopressor agent, norepinephrine, phenylephrine, epinephrine, dopamine, vasopressine or its analogs, and soever. When a patient will die on vasopressor therapy, the corresponding vasopressor free day will be 0.

3) Mechanical ventilation free days: defined as the number of days with permanent appropriate oxygenation while the patients is extubated and breathing spontaneously, i.e. no need for non invasive ventilation, high flow oxygen or CPAP. Other uses of non-invasive ventilation (e.g., chronic night-time use for chronic obstructive pulmonary disease) are not counted. When a patient will die on mechanical ventilation or will be discharge home on mechanical ventilation, the corresponding mechanical ventilation free day will be 0.

4) Organ dysfunction free days: Organ function (including renal function) will be assessed by the SOFA score (Vincent 1996). Organ dysfunction will be defined by a SOFA score of > 6 (Annane 2018). Organ dysfunction free days are defined by the number of days with os total SOFA score of 6 or less. When a patient will die on vasopressor therapy, the corresponding vasopressor free day will be 0.

5) HRQoL in 6-month survivors assessed by the EuroQol-5D (EQ-5D). This questionnaire is a standardised measure of health status developed to provide a simple, generic measure of health for clinical and economic appraisal. It is made up for two components; health state description and evaluation. The health status is measured in terms of five dimensions; mobility, self-care, usual activities, pain/discomfort, and anxiety/depression. In evaluation part, the respondents evaluate their overall health status using the visual analogue scale. See Figure 4.

6) Proportion of patients with a decision to withhold and/or withdraw active treatments

7) ICU and hospital length of stay

8) Rate of re-admission to the ICU during the 180 days after randomization

9) Safety endpoints:

- Proportion of patients affected by any serious adverse events associated with corticosteroids, among the following: hospital-acquired infections, hyperglycemia, hypernatremia, neurological disorders (coma, stroke or muscle weakness, as defined below) during the 90 days after randomization
- Coma will be defined as a Glasgow coma score < 8

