9 STATISTICAL ANALYSIS

9.1 SAMPLE SIZE DETERMINATION

We will enroll a total of at most 1800 patients. Sites are expected to enroll at least 1 or 2 patients per month.

Adaptive outcomes

The goal is to develop an adaptive clinical trial design which evaluates the therapeutic intervention of targeted therapy, identifies subset of subjects who respond better to the experimental therapy.

Sequential analyses will use the number of vasopressor-free days at day 28 as the measure of efficacy, and the occurrence of severe adverse events within the first 28 days as the measure of toxicity. According to the literature (the APPROCCHS trial), the number of vasopressor-free days at day 28 in the hydrocortisone+fludrocortisone group was 17.1 ± 10.8 versus 15.0 ± 11.1 in the placebo group. Thus, a sample of 176x2=352 patients achieves 80.04 % power to reject the null hypothesis of equal means when the mean difference between arms is 3 days with SD of 10 days, and with a significant level (alpha) of 0.05 using a two-sample t-test. For interactions to be detected with the same power as the overall effect, sample sizes should be inflated (Brookes 2004); estimated here at a multiple of fourfold; therefore, to handle potential dropouts, a sample of 1800 patients was considered to be enrolled.

Note that Bayesian inference will be used for sequential analyses, so that no inflation of type I error rate is to be corrected.

Primary outcome

To detect a 10% absolute risk reduction (from 45% to 35%) in the day 90 mortality, a sample size of 373 evaluable patients per arm (thus a total of 746 patients) is required to reach a 80% power. The planned sample of 1800 patients will achieve a 99.16%

power to reject the null hypothesis of equal mortality when the difference between arms is 10% overall, and with a 5% alpha level.

Sample sizes were computed using PASS 15 software (2017).

The power to detect this difference within each group of analysis will depend on the prevalence of each biomarker of interest.

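### Secondary objective 8 defines the cognitive outcome only as a low PROMIS score: a yes/no cut of a graded scale, with no reason, cut-off or time point in the text at hand and no matching outcome in section 5.14.2

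*Protocol*

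**What the plan says.** Protocol section 2.2 lists the outcomes on which the arms are to be compared, separately for each biological marker. Item 8 is "neurological cognitive dysfunction defined as by low score on the PROMIS Adult cognitive function score", with a pointer to appendix 15.4.7. In the text at hand that appendix appears by title only, in the list of addenda.

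The neighbouring items that use a threshold state it: item 4 (glucose), item 5 (sodium) and item 9 (MDRS grade 2 or more). Item 2, quality of life at 6 months, is left uncut.

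The Study summary describes the same domain without a cut: "Daily cognitive function and muscles' strength (days 1 to 28, 90 and 180 days".

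Section 5.14.2, the list of secondary outcomes, has no PROMIS or cognitive outcome. Its composite safety endpoint covers "neurological disorders (coma, stroke or muscle weakness, as defined below) during the 90 days after randomization", and the list adds the MDRS and the Glasgow coma scale.

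PROMIS is collected as an instrument. Section 5.5 lists it at days 90 and 180. In the section 5.8 schedule, the row shared by EQ-5D-5L and PROMIS is marked at day 1, day 28, day 90 and 6 months.

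**The concern.** Item 8 is the only place where the protocol says what the cognitive outcome is, and it says it as a cut. The graded score will be in the database anyway, so comparing the arms only on low versus not low gives up information already paid for in questionnaires and calls.

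Two things are at stake. A moderate shift in cognition would more often go undetected, most of all in the biomarker cohorts. Section 9.1 itself says that power within each group depends on how common the biomarker is. The result would also depend on where the cut is placed, and the text shown does not place it.

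The gap in section 5.14.2 adds to this: no second definition is available to fall back on.

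**Working it through.** **1. The plan's own figures.** Section 9.1 gives no power, effect, SD, prevalence or sample size for PROMIS. Its figures for other outcomes can be checked, to confirm the formulas.

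- For the primary outcome: "a sample size of 373 evaluable patients per arm (thus a total of 746 patients) is required to reach a 80% power". Two-sided 0.05, unpooled variance: (1.960 + 0.842)² × (0.45×0.55 + 0.35×0.65) / 0.10² = 372.8, so 373 per arm. Pooled variance gives 376, the figure in the Study summary.
- At 900 per arm the unpooled formula gives 99.16%, as stated.
- For vasopressor-free days (difference 3, SD 10, 176 per arm) a two-sample t-test gives 80.1%, against the stated 80.04%.

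The protocol's alpha is 0.05 with no sidedness stated. Two-sided reproduces its figures and is used below.

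**2. Information kept by a cut.** Assume a normal score and a small uniform shift. A cut that puts a fraction q of controls in the low group has efficiency φ(z_q)² / [q(1−q)] relative to the full score.

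| Cut | q | Information kept |
|---|---|---|
| control median | 50.0% | 64% |
| 0.5 SD below mean | 30.9% | 58% |
| 1 SD below | 15.9% | 44% |
| 1.5 SD below | 6.7% | 27% |

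The figure drops below one half only when about 21% or fewer of controls score low.

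**3. Power, as an illustration.** All PROMIS inputs are assumptions. Take a shift d = 0.20 SD and n = 373 per arm, a number borrowed from the primary outcome.

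- Full scale: Φ(d√(n/2) − 1.96) = Φ(2.731 − 1.96) = 78.0%.
- After a cut at c SD from the control mean: p_control = Φ(c), p_treated = Φ(c − d) for benefit, then a two-proportion test.
- Worked case, c = 0: proportions 0.500 and 0.4207, difference 0.0793. The standard error is 0.0365 under the null and 0.0364 under the alternative. Power = Φ[(0.0793 − 1.96×0.0365)/0.0364] = 58.4%.

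| Cut | Low, control / treated | Power | Loss (points) | Loss if the shift is towards harm, Φ(c + d) |
|---|---|---|---|---|
| median | 50.0% / 42.1% | 58% | 19.6 | 19.6 |
| 0.5 SD | 30.9% / 24.2% | 53% | 25.0 | 21.9 |
| 1 SD | 15.9% / 11.5% | 41% | 37.0 | 31.6 |
| 1.5 SD | 6.7% / 4.5% | 26% | 51.7 | 45.9 |

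**4. How far this moves with the assumptions** (benefit direction).

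| n per arm | Shift (SD) | Full-scale power | Loss: median cut | Loss: 1 SD cut | Loss: 1.5 SD cut |
|---|---|---|---|---|---|
| 900 | 0.30 | about 100% | 0.1 | 2.4 | 15.6 |
| 900 | 0.20 | 98.9% | 6.7 | 22.1 | 45.0 |
| 585 | 0.20 | 92.8% | 15.1 | 34.5 | 54.6 |
| 495 | 0.20 | 88.2% | 17.6 | 36.8 | 55.0 |
| 176 | 0.30 | 80.4% | 19.7 | 39.2 | 54.6 |
| 176 | 0.10 | 15.3% | 4.1 | 6.5 | 8.5 |

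The rows for 585 and 495 are survivors at full enrolment under the planned 35% and 45% mortality (900×0.65 and 900×0.55). The loss is small where power is near 100% or very low either way, and large in between.

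**The case against.** The best defence has four parts.

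- Section 2.2 states objectives, not analyses. No test or model is fixed for PROMIS, nothing rules out a graded analysis, and section 4.5.2 announces a full statistical analysis plan. This stands in part: that plan may add a graded comparison, and appendix 15.4.7 may give the cut-off. So it would be wrong to infer that the trial has no cut-off or will not analyse the score. But a graded analysis there would depart from the only operational definition in the protocol.
- Items 4 to 9 read as a block of possible harms, each framed as whether a condition occurs. The incidence of dysfunction is a legitimate question, and harm concentrated in already impaired patients would not follow a uniform shift. This stands, and it is why the proportion should be kept. It does not justify using the proportion alone.
- A reader might infer that the cut throws away most of the information. The documents do not support that: a cut at the median or near the 30% point keeps 58% to 64%, and the raw score is still collected.
- A reader might infer one figure for the power lost in this trial. None can be given, because the effect, SD, cut-off and number evaluable for PROMIS are all absent.

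No sample size rests on this endpoint, which limits the stakes.

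**Conclusion.** The point holds as a minor, inexpensive improvement to a secondary endpoint. The protocol's only definition of the cognitive outcome is a yes/no cut of a graded score. The text shown gives no reason, cut-off or time point for it, and the section 5.14.2 outcome list omits cognition altogether.

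Under normality and a uniform shift, the cut gives up about 36% to 73% of the information, depending on where it falls. In the illustrative case of 0.20 SD and 373 per arm, power drops from 78% to between 58% and 26%. Elsewhere the loss runs from about zero (900 per arm, 0.30 SD, median cut) to more than 50 points (extreme cuts), and away from the median it is somewhat smaller if the shift is towards harm. These figures show how the loss behaves; they are not estimates for this trial. The primary outcome and the planned sample size are not affected.

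**What to change.** - Reword section 2.2, item 8, so that the PROMIS cognitive score is compared between arms on its full scale, by a mean difference or by a rank-based or proportional-odds comparison if the score is skewed. Name days 90 and 180 as the main time points.
- Keep the proportion with a low score as a companion, with its cut-off stated in the item or by a reference to where it is defined.
- Add the outcome to section 5.14.2.
- Keep the other scheduled PROMIS assessments and reconcile the schedules. The Study summary says daily to day 28, then days 90 and 180; section 5.8 marks days 1, 28, 90 and 6 months; section 5.5 lists days 90 and 180.

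The cost is a few lines of text and the matching line in the statistical analysis plan, with no new patients, visits or questions. The one drawback is that a difference in score is harder to interpret than a proportion, and the companion proportion covers that.

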3 STUDY DESIGN

The RECORDS multicentre trial will be conducted within two stages. First, the run-in non-interventional, observational period will last 6 month. During this period, eligible patients will be treated with hydrocortisone and fludrocortisone. The clinical and laboratory data will be collected. This period will allow refining the incidence of elligible patients in participating centres and defining the biomarkers on which the interventional period will be based.

In addition, during this phase, we will retrospectively include COVID patients who were managed during the health crisis and who were collected as part of care within 3 months prior to the start of the research.

The second period will be interventional and last 54 months. This stage will be a multicentre concealedallocation multi-arms, parallel-group, adaptive blinded RCT. Patients will be randomly assigned to hydrocortisone plus fludrcortisone or placebos for 7 days. Our maximum recruitment target is 1800 patients with full follow-up. Since loss to follow up is rare in critical care trials with outcomes measured at day 90, we do not expect missing data for the primary outcome. Study personnel at the clinical sites will document the composite of death or persistent organ dysfunction at day 90.

The sites will include on average 1 patient per month over 48 months of inclusion and 6 months of followup.

4 METHODS

4.1 STUDY SETTING

This study will be centrally coordinated by Paris IIe de France Ouest Clinical Research Unit (URC HUPIFO) attached to the Delegation of Clinical Research and Innovation (DRCI) of The Paris Public Hospital Assistance (APHP), at the Hospital Raymond Poincaré, IIe de France, France. URC PIFO will be responsible for programming and maintaining the randomization system and the electronic data capture (EDC) system. The Centre de Ressource Biologique (Biological resource centre) at the Hospital Ambroise Paré, Paris Saclay Ouest will be responsible for managing the storage and analysis of the blood samples. The RECORDS Trial will be conducted in French adult general ICUs, including sites from CRICS-TRIGERSEP, a F-CRIN labelled sepsis network.

The study will be conducted in two phases: an observational phase and an interventional phase.

14/61

4.1.1 Observational phase (run-in period)

The observational phase (Run in period) lasts at least 6 months. Its aim is to collect as much information as possible on biomarkers likely to influence responses to corticosteroids under the usual conditions of care and develop reference values for the biomarkers. These values will later be used during the second phase (interventional phase) to set up diagnostic tests in order to rapidly identify patients with sepsis who may be sensitive or resistant to corticoids

During the first stage, run-in observational period, all participants will receive as a standard of care, openlabeled, commercialized hydrocortisone and fludrocortisone, or dexamethasone or methylprednisolone, at equivalent doses, or no corticosteroids as left at physician discretion. Physicians will be asked to strictly follow before prescribing corticosteroids all available information on contraindications, caution in use and drug-drug interaction by referring to http://base-donnees-publiques.medicaments.gouv.fr. Hydrocortisone will be given as a 50mg intravenous bolus every 6 hours (6 to 8 mg equivalent of dexamethasone once daily, 40mg per day equivalent of methylprednisolone on continuous intravenous infusion) for seven days and fludrocortisone will be given orally/enteraly as a 50µg tablet once a day (in the morning) for seven days. Patients with COVID-19 will receive dexamethasone 6 mg once daily for 10 days (RECOVERY 2020), or equivalent dose of hydrocortisone (150 to 200mg), according to e recent WHO propective meta-analysis for corticosteroids in COVID-19 (Sterne 2020).

All consecutive eligible patients should be approached for participation in the run-in observational part of the study by the clinical investigators or person qualified to carry out the research. The clinical investigator will inform the eligible person of this study then collect the consent of this person to use his/her clinical data and biological samples routinely collected for the present research. If the patient is unable to confirm or not his/her consent within the time window allowed by the protocol, his or her authorized persons (members family, curator, guardianship, trusted person) may be approached in person4. The local research team could also enroll eligible patients.

For the observational phase, patients with Covid 19 who met the eligibility criteria as below, can be retrospectively included in the observational cohort. For these patients, we will use data from the analysis of samples collected as part of their care in the participating centres. The inclusion of this retrospective cohort may help shortening the duration of the run in period and may accelerate the identification of biomarkers to be investigated in the interventional phase.

4.1.1.1 Eligibility Criteria (observational phase)

The patients included in this phase should present the following selection criteria:

4. 1. 1.1.1 Inclusion Criteria (observational phase)

- Patients ≥18 years old;
- Admitted to ICU with proven or suspected infection as the main diagnosis;
- Community acquired pneumonia related sepsis OR vasopressors dependency (norepinephrine, epinephrine, vasopressin, dopamine, phenylephrine) OR septic shock (Singer 2016: vasopressor to maintain mean blood pressure of at least 65 mmHg and lactate levels above 2 mmol/l) OR acute respiratory distress syndrome (ARDS Ranieri 2012: a- acute onset, i.e. within one week of an apparent clinical insult and with progression of respiratory syndrome, b- bilateral opacities on chest imaging not explained by other pulmonary pathologies, e.g. pleural effusion, atelectasis, nodules etc, c- no evidence for heart failure or volume overload, d- PaO2/FiO2 ≤ 300 mm Hg, PEEP ≥ 5 cm H2O
- Patient who has signed an informed and written consent whevener he/she is able of consent, if not, if not ascent from his/her representant whenever he/she is present at time of screening for inclusion

- Affiliation to a social security system or to an universal health coverage (Couverture Maladie Universelle, CMU).
- Patients under guardianship or curatorship will be included.
- Patients in case of simple emergency (legal definition) will be included.
- Patients managed with covid 19 and having biological samples available

4.1.1.1.2 Exclusion Criteria (observational phase)

- Pregnancy;
- Expected death or withdrawal of life-sustaining treatments within 48 hours;
- Previously enrolled in this study

The observational phase poses no risk to participants. Any adverse reactions observed in the patients during this phase are reported by the investigators as per the local vigilance procedures. All adverse events will be recorded in the patient case report form (eCRF).

4.1.2 Interventional phase

4.1.2.1 ELIGIBILITY CRITERIA (INTERVENTIONAL PHASE)

4.1.2.1 Inclusion Criteria (interventional phase)

- 1) Patients \geq 18 years old;
- 2) Admitted to the ICU with proven or suspected infection as the main diagnosis;
 - 3) Community acquired pneumonia related sepsis OR vasopressors dependency (norepinephrine, epinephrine, vasopressin, dopamine, phenylephrine) OR septic shock (Singer 2016: vasopressor to maintain mean blood pressure of at least 65 mmHg and lactate levels above 2 mmol/l) OR acute respiratory distress syndrome (ARDS Ranieri 2012: a- acute onset, i.e. within one week of an apparent clinical insult and with progression of respiratory syndrome, b-bilateral opacities on chest imaging not explained by other pulmonary pathologies, e.g. pleural effusion, atelectasis, nodules etc, c- no evidence for heart failure or volume overload, d-PaO2/FiO2 ≤ 300 mm Hg, PEEP ≥ 5 cm H2O

4) Patient who has signed an informed and written consent whevener he/she is able of consent, if not, if not ascent from his/her representant whenever he/she is present at time of screening for inclusion

- 5) Patients who have been tested for one or more RECORDS specific biomarkers
 - o CIRCI
 - o Endocan
 - o GILZ <
 - o CPD
 - o Transcriptomic SRS2
 - o Endotype B
 - o PCR COVD-19
 - o PCR Influenza
 - o PCR other respiratory virus

6) Affiliation to a social security system or to an universal health coverage (Couverture Maladie Universelle, CMU);

7) Patients under guardianship or curatorship will be included;

8) Patients in case of simple emergency (legal definition) will be included.

RECORDS" protocol, version 4.0 of 03/03/2021

16/61

